Patients will be recruited through advertisement, as well as clinician referral and self-referral. Self-referred patients will call the study sites and will be screened over the phone by the study coordinators. Those deemed potentially eligible will be scheduled for a screening visit with one of the study physicians at the sites. Based on clinical and human subject protection considerations, a potential subject will, under no circumstance, be advised to taper his/her current medication regimen prior to the screening visit.

Subjects will also be recruited through physician referral. Each site will recruit subjects via referral from primary care and specialty clinics from the communities surrounding each study site. Each site will utilize the experience of the MGH CCC to conduct outreach activities to community organizations, colleges, and other resources. Sites will regularly collaborate on strategies to recruit women and minorities, and sites will employ strategies specific to their local community, in ways that are culturally sensitive and specific to the local minority population. Retention will be enhanced with fair reimbursement (as deemed appropriate by the local IRB) for subjects' time. Site specific recruitment details are located in each site's recruitment plan.

E.2. Number of Subjects

We expect to screen approximately 300 patients to randomize up to 55 patients.

When the randomization target has been met, patients who have been screened but not yet randomized will be allowed to continue in the study unless they fail to meet randomization criteria.

E.3. Nature of Populations

Subjects must meet all of the following inclusion and none of the exclusion criteria ([Section G.4.](#)) to be eligible for participation in the study.

Protocol waivers for eligibility will not be granted under any circumstances. If, during the course of a subject's post-randomization participation in the trial, it is discovered that the subject did not meet all eligibility criteria, the justification to allow the subject to continue in the trial will be made by the PPI, with medical input from the Medical Monitor and the site's investigator(s), and will be documented in the patient's record. Whether or not the participant is allowed to remain in the trial, this will be reported as a major protocol deviation and not a waiver.

E.4. Subject Eligibility

E.4.1. Inclusion Criteria

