A patient who remains in the study for the first two treatment periods or for all four treatment periods will receive a balanced exposure to treatments randomized to receive. If patients discontinue treatment prior to completing the entire 24 weeks of study, all their data (including weekly assessments) from their time in the study will be used in the analyses. Because the main analysis is based on maximum likelihood estimation using a mixed-effects multi-period crossover model, the inferences will be unbiased under missing at random assumptions. No imputation of missing data is planned for this study, unless intensive investigations indicate that reliable and valid data imputation is possible, in which case multiple imputation will be performed and the analysis of the imputed data sets will serve as a sensitivity check of the results from the primary analysis based on the mixed-effects models (van Buuren et al, 2011).

All analyses will adjust for age, sex, K-L grade, and site.

All hypothesis tests will be two-sided using 5% significance level, and *p*-values unadjusted for multiple testing will be reported. The justification for this decision is that this is a Phase II investigation and all assessed outcomes are of specific and unique interest. Much more important than testing hypotheses is the efficient estimation of all quantities of interest, and this will be carried out throughout the analyses. Point estimates, 95% confidence intervals and standardized effect sizes (e.g., Cohen's *d*) will be reported for all estimated effects, regardless of whether the null hypotheses were rejected or not.

K.2. Hypothesis testing

Aim 1: Assess the safety of CNTX-6970 (300mg BID).

There will be no formal hypothesis testing under Primary Study Aim 1. All AEs and SAEs observed during different treatment periods will be summarized based on severity and relation to the active treatment (CNTX-6970 300mg BID). The reports will include tabulation of the AEs and SAEs by period, block, and treatment; point estimates and 95% CIs will be reported. Similarly, we will summarize relevant laboratory measures (see Section F.2.1) with appropriate estimates.

Aim 2: Assess the efficacy of CNTX-6970 (300mg BID) in comparison to placebo with respect to the primary outcome measure for pain due to osteoarthritis of the knee - WOMAC Part A.

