## 5.3 Randomization and Blinding

For entry into the study and randomization, all eligibility criteria MUST be met (i.e., all inclusion criteria and no exclusion criteria specified in the protocol). Patients who meet inclusion/exclusion criteria at the Baseline Visit (day 0) will be randomized. After documentation of written informed consent and the screening period, clinical sites will confirm eligibility and complete randomization by accessing the Almac's centralized web-based system for randomization and drug management - the Interactive Web Response System (IXRS). Subjects will be randomized equally between treatment sequences shown in Figure 1: Drug:Placebo:Placebo:Drug or Placebo:Drug:Drug:Placebo. A standard block randomization will be used, stratifying by K-L grade (stratum 1 K-L grade 1 or 2, and stratum 2 K-L grade 3 or 4) to achieve balance on randomization sequences. The randomization will be implemented by the IXRS vendor in consultation with the study statisticians. After Randomization, drug will be dispensed.

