## 6 Sample Size

The sample size for this study was determined based on the primary efficacy aim to detect clinically meaningful and realistic effects of CNTX-6970 (300 mg BID) compared to placebo in the multi-period crossover

design model. Power was computed for effect sizes ranging from 0.25 to 0.50 using Monte Carlo simulation. Data were simulated from multi-period crossover models with block, period, and carryover effects, and varying within and between subject variability.

Although carryover effects can be efficiently isolated and estimated in the analysis stage by using the mixed-effects models proposed in Section 7, power for the primary hypothesis was computed using only WOMAC-A assessed during the last 2 of 6 weeks per treatment period to minimize carryover effects. The power of the test depends on the relationship of the between-subject variability to the within-subject variability. In general, the between-subject variability is larger than the within-subject variability, but a range of Between/Within (B/W) variance ratios (5/1, 2/1) were investigated. With a sample size of  $n = 55$  per arm, using a two-sided Type I error rate of  $\alpha = 0.05$ , the power to detect an effect size (for the active treatment vs. placebo) of Cohen's  $d = 0.35$  exceeds 95% when the ratio  $B/W = 2/1$ .

Assuming a 15% early termination (e.g., dropout) rate during each of the 4 periods will yield a sample size of approximately  $n = 29$  with complete observations at all treatment periods. If we conservatively assume that only subjects with complete data will be analyzed, the corresponding power with  $n = 29$  exceeds 80% when the ratio  $B/W = 2/1$  with an effect size as low as 0.30. Figure 2 shows the results of a simulation study to evaluate the power of this design. Because we will use all available data from all enrolled subjects in the analysis, the actual power in the case of 15% early termination per treatment period will be larger than what Figure 2 shows. If the ratio B/W is larger than 2, say B/W=3, 4 or 5, the power for detecting the treatment effects is much larger. For example, with only 29 participants, if B/W=5, the power to detect an effect of magnitude Cohen's  $d = 0.35$  exceeds 0.95. Note that the reported test-retest reliability of the WOMAC-A measure is 0.86, which corresponds to a  $B/W = 7$ .

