### 7.3 Covariates and Subgroups

All analyses will adjust for K-L grade, age, sex, and site (as a random effect if the data is sufficient to model a site random effect).

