For PGIC, this instrument asks if the overall pain since the start of the study is “Very much improved” (score 0), “Much improved” (score 1), “Minimally improved” (score 2), “No Change” (score 3), “Minimally worse” (score 4), “Much worse” (score 5), “Very much worse” (score 6). The analysis for outcome (c) PGIC will use a proportional odds regression with outcome PGIC at week 24 (V9), controlling for treatment, age, sex and baseline WOMAC-A; this model will not control for week 3 PGIC since the instrument is asking about the change in pain. Note also that the treatment in the last period is the same treatment as in the first period, so a comparison of the active to the placebo in terms of change in pain can be done using week 24 PGIC outcomes for the two different treatment sequences used in this trial. The analysis plan for outcome (e) will follow the same approach as in aim 4 below.

**Aim 4.** Outcomes (a)-(f) are assessed at baseline and week 24. Testing hypotheses for these outcomes will not benefit from the multi-period crossover design because they are assessed only at baseline and week 24. Instead, we will test the hypotheses by comparing subjects taking active drug versus placebo at the last treatment period ending on week 24. Regressions will be used to model the outcome at week 24 as a function of treatment, the baseline level of the outcome, age, sex and K-L Grade. A standard linear regression will be used for continuous outcomes; a proportional odds model will be used for the non-binary ordinal outcomes defined by discrete categories (e.g., PHQ-2, GAD) and logistic regression models will be used for binary outcomes (e.g., OUQ).

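### The week-24 PGIC model omits K-L grade and site against the plan's own rules, and week-3 PGIC, the only one scheduled before any crossover, has no analysis as an outcome

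*SAP*

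**What the plan says.** **PGIC model.** SAP 9.2 (Aim 3, outcome (c)) fits a proportional-odds regression to PGIC at week 24 (V9), "controlling for treatment, age, sex and baseline WOMAC-A". It adds that "this model will not control for week 3 PGIC since the instrument is asking about the change in pain". It justifies the week-24 comparison by noting that in both sequences the last-period treatment is the same as the first-period treatment.

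**Covariate rules.** SAP 7.3 states: "All analyses will adjust for K-L grade, age, sex, and site", with site as a random effect if the data can support one. Protocol K.1 gives the same four covariates for all analyses. Protocol K.2 says PGIC follows the Aim 4 approach, and the Aim 4 regression in SAP 9.2 lists K-L grade. SAP 5.3 makes K-L grade (1–2 against 3–4) the randomisation stratum.

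**Timing.** The schedule of events and SAP 9.2 place PGIC at week 3 and week 24 only. SAP 9.2 describes the item as asking about overall pain since the start of the study. The sequences are Drug:Placebo:Placebo:Drug and Placebo:Drug:Drug:Placebo, in 6-week periods (SAP 5.1 and 5.3).

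**Visit 9.** Protocol F.1.14 makes V9 the week-24 or early-termination visit and lists PGIC there. Protocol F.3.2 ranks PGIC third on the shortened telephone list for patients who decline that visit.

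**The concern.** There are three gaps.

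1. The PGIC covariate list departs, without a stated reason, from rules that cover it. If both texts stand at database lock, an analyst can defend a model with or without the stratification factor after seeing the results.
2. Week-3 PGIC is collected under Hypothesis 2(c) but has no outcome analysis. The SAP's reason, that the item already measures change, bears on its use as a covariate and not on its use as an outcome. Matching first and last treatments does not deal with the 12 weeks on the opposite treatment in between. A single between-sequence comparison at week 24 cannot separate current treatment from that history.
3. The SAP does not say whether early-termination values recorded at V9 enter the week-24 model, or under which treatment.

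**Working it through.** **Covariates, side by side**

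| Source | K-L grade | Site |
|---|---|---|
| SAP 9.2, PGIC model | not listed | not listed |
| SAP 7.3, all analyses | required | required if the data allow |
| Protocol K.1, all analyses | required | required |
| SAP 9.2, Aim 4 model (to which protocol K.2 sends PGIC) | listed | not listed |

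K-L grade is called for by all three governing texts. Site is called for by two of them.

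**Exposure by sequence (weeks)**

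| Sequence | 0–6 | 6–18 | 18–24 | Total by week 24 |
|---|---|---|---|---|
| Drug first | drug | placebo | drug | 6 + 6 = 12 drug, 12 placebo |
| Placebo first | placebo | drug | placebo | 12 drug, 6 + 6 = 12 placebo |

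At week 24 each group has just spent 12 consecutive weeks on the other treatment. At week 3 each patient has received only the first assigned treatment, for 3 weeks.

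**Numbers available.** Inputs: up to 55 randomised (protocol E.2; SAP section 6) and the SAP's planning assumption, "Assuming a 15% early termination (e.g., dropout) rate during each of the 4 periods".

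- Reproducing the SAP's complete-data figure: 55 × 0.85⁴ = 28.7, which rounds to its 29. The protocol's 26 from 50 also reproduces: 50 × 0.85⁴ = 26.1.
- Week 24: about 29 if only patients with complete data count. If early-termination V9 values are used, N could rise as far as 55.
- Week 3: the documents give no figure. Assuming attrition is even within period 1, 55 × 0.85^0.5 = 50.7, about 51.

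**Power of a between-sequence comparison.** Two-sided 5% (protocol K.1), 1:1 allocation, normal approximation: power = Φ(d√N/2 − 1.96). No PGIC effect size is given, so d is taken from the 0.25–0.50 range that SAP section 6 uses for WOMAC-A.

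| d | N = 29 | N = 51 | N = 55 |
|---|---|---|---|
| 0.25 | 10% | 14% | 15% |
| 0.35 | 15% | 24% | 25% |
| 0.50 | 27% | 43% | 46% |

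At d = 0.35 and N = 29: 0.35 × √29/2 − 1.96 = −1.02, and Φ(−1.02) is about 0.15. The difference detectable with 80% power, (1.96 + 0.84) × √(4/N), is about 1.04 at N = 29, 0.78 at N = 51 and 0.76 at N = 55.

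**Sensitivity to a smaller effect at week 3.** Even with N = 29 at week 24, the week-3 effect that gives the same power is 0.35 × √(28.7/50.7) = 0.26. A week-3 effect about a quarter smaller therefore removes any gain from the larger N.

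**Early termination.** The SAP's argument that first and last treatments match holds only in period 4. A patient who stops in period 2 or 3 was on the opposite of the first-period treatment. One who stops in period 1 has never crossed over. SAP 7.4 uses data up to the time of discontinuation, which does not settle whether a V9 value recorded after stopping is included.

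**The case against.** A reader might infer that week 24 rests on 29 patients against 51 at week 3, with 15% against 24% power, and that week 3 should therefore lead. The documents do not support this:

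- The 29 is a planning count of patients with complete WOMAC-A data, and V9 also collects PGIC from early leavers. At N = 55, week-24 power is about 25%, so the gap closes.
- The 51 rests on an assumed pattern of attrition.
- Equal effects at the two times are also assumed. Week 3 is mid-period, protocol D.1 looks for separation from placebo by 6 weeks, and the primary analysis uses only the last two weeks of each period.

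A reader might also infer that pharmacological carryover distorts week 24. That is not shown. Week 24 is six weeks into the last period, protocol K.2 cites a mean half-life of 15.8 to 16.6 hours, and both documents regard four weeks as ample washout. What stands is narrower: patients with 12 weeks of each treatment are asked about change since the start of the study.

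Nor do the documents show that K-L grade was removed on purpose, or that it predicts PGIC. The omission is a contradiction to reconcile, and no loss of precision can be quantified.

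Finally, a second PGIC result at an unadjusted 5% level adds multiplicity unless its role is fixed in advance. That is a fair point, and it is why week 3 should be labelled supportive. First-period comparisons are not foreign to this plan: under Aim 5 the SAP already models week-6 synovial fluid on first-period treatment.

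**Conclusion.** The point holds in this form. The omission of K-L grade and site can be read directly from the text and conflicts with SAP 7.3 and protocol K.1; for K-L grade it also conflicts with the Aim 4 routing. Week-3 PGIC is the only scheduled PGIC before any crossover, and it has no outcome analysis. Handling of early-termination values at V9 is unspecified, which leaves the week-24 N anywhere from about 29 to 55.

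Week 24 should remain the test of Hypothesis 2(c). The case for reporting week 3 is interpretability, not power: at d = 0.35, power is about 15–25% at week 24 and about 24% at week 3, so neither is well powered. These figures depend on 15% loss per period, even attrition within period 1 for the week-3 count, and an effect size borrowed from WOMAC-A.

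**What to change.** Amend SAP 9.2 before unblinding:

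1. Add the two-level K-L stratum to the week-24 PGIC proportional-odds model, and site where the data allow, as 7.3 provides. If site is dropped, say so and why.
2. Keep week 24 as the test of Hypothesis 2(c). Fit the same model to week-3 PGIC by first-period treatment and report it beside week 24 as a supportive analysis, noting that it reflects only 3 weeks of treatment.
3. State whether early-termination V9 values enter the week-24 model and, if so, which treatment they are assigned to.

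The cost is a few SAP sentences and one extra model fit. All the data are already collected. The K-L stratum uses one model parameter. A site effect may not be estimable with this many patients, and 7.3 already allows for that.

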Outcomes (a) and (f) are assessed at baseline and each study visit through week 24. Outcome (b) will be assessed at each in-person visit except baseline. Outcome (c) will be assessed at week 3 and week 24 only. Outcome (d) will be assessed at baseline and each in-person visit through week 24. Outcome (e) will be assessed at baseline and week 24 only. The analysis plan for outcomes (a), (b), (d), and (f) will be similar to the analysis for aim 2 except that the model will adjust for possible carryover effects in placebo-treated periods that are preceded periods with the active drug treatment; the analysis plan for outcomes (c) and (e) will follow the same approach as in aim 4 below.

Aim 4: Assess the efficacy of CNTX-6970 (300mg BID) in comparison to placebo with respect to general outcomes of pain: (a) Pain Catastrophizing Scale –Short Form 6, (b) PROMIS Physical Functioning Short-Form 6b, (c) Patient Health Questionnaire (PHQ) – Depression, (d) Generalized Anxiety Disorder – 2 item scale (GAD-2); (e) Tobacco, Alcohol, Prescription medication, and other Substance use Tool (TAPS-1); and (f) Opioid Use Questionnaire.

HYPOTHESIS 3: CNTX-6970 300mg BID is superior to placebo with respect to outcomes measured by (a) Pain Catastrophizing Scale –Short Form 6, (b) PROMIS Physical Functioning Short-Form 6b, (c) Patient Health Questionnaire (PHQ) – Depression, (d) Generalized Anxiety Disorder – 2 item scale (GAD-2), (e) Tobacco, Alcohol, Prescription medication, and other Substance use Tool (TAPS-1), and (f) Opioid Use Questionnaire.

Outcomes (a)-(f) are assessed at baseline and week 24. Testing hypotheses for these outcomes will not benefit from the multi-period crossover design because they are assessed only at baseline and week 24. Instead, we will test the hypotheses by comparing subjects taking active drug versus placebo at the last treatment period ending on week 24, controlling for the baseline value of the outcome.

Aim 5: Assess the efficacy of CNTX-6970 (300mg BID) in comparison to placebo with respect to biomarkers of pain and inflammation: (a) Staircase-Evoked Pain Assessment, (b) Serum and synovial fluid levels of chemokines and cytokines; and (c) Synovial monocyte chemoattractant protein-1/CCR-2 receptor binding inhibition in blood and synovial fluid.

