HYPOTHESIS 4: Compared to placebo, CNTX-6970 300mg BID will result in more improvement with respect to (a) Staircase-Evoked Pain Assessment, (b) Serum and synovial fluid levels of chemokines and cytokines; and (c) Synovial monocyte chemoattractant protein-1/CCR-2 receptor binding inhibition in blood and synovial fluid.

The Staircase-Evoked Pain Assessment will be assessed at Baseline and each in-person study visit through Week 24 (Week 3, 6, 9, 12, 15, 18, 21, and 24/ET visits).

Hypothesis 4 will be tested with the same approach as for testing the hypotheses under Aim 3.

K.3. Exploratory analyses

Aim 6. If CNTX-6970 is more effective than placebo, evaluate the following characteristics of its effect: (a) onset of action; (b) carryover effect after treatment discontinuation.

We will study the change of symptoms over time using a time trend in our statistical models within each of the 6-week treatment periods to model the weekly WOMAC-A measure.

Under this aim, the interest is not in hypothesis testing, but rather in understanding the progression and magnitude of onset of action and the carryover effects of the CNTX-6970 compound. This approach will allow an elucidation of the nature of action of the compound.

Aim 7. Identify biomarkers related to pain from OA of the knee, course of the disease, and response to treatment with CNTX-6970.

Statisticians on the study team have published methods for analysis of complex multimodal data, such as EEG and brain imaging for developing optimal treatment decision (e.g., Ciarleglio et al, 2018; Jiang et al, 2020; Park et al, 2020a; Park et al, 2020b; Petkova et al, 2020), one of the objectives of precision medicine. Although this previous work has been primarily motivated by mental health research (e.g., depression), the methodologies developed apply equally to pain and other medical conditions. As necessary, new methodologies will be developed for the joint analysis of outcome measures.

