**Aim 5:** Assess the effect of CNTX-6970 (300mg BID) in comparison to placebo with respect to biomarkers of pain and inflammation: (a) Staircase-Evoked Pain Assessment; (b) serum and synovial fluid levels of chemokines and cytokines; and (c) synovial monocyte chemoattractant protein-1/CCR-2 receptor binding inhibition in blood and synovial fluid.

**HYPOTHESIS 4:** Compared to placebo, CNTX-6970 300mg BID will result in greater improvement with respect to (a) Staircase-Evoked Pain Assessment; (b) serum and synovial fluid levels of chemokines and cytokines; and (c) synovial monocyte chemoattractant protein-1/CCR-2 receptor binding inhibition in blood and synovial fluid.

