### 9.2 Secondary Efficacy Analyses

The outcomes for Aims 3, 4 and 5 in Section 4 are assessed at multiple time points throughout the study.

**Aim 3.** Outcome (a) WOMAC-C is assessed at baseline and each study visit through week 24. Outcome (b) HADS (anxiety and depression scales which will be modeled separately) is assessed at in-person visits except baseline. Outcome (c) PGIC is assessed at week 3 and week 24 only. Outcome (d) PROMIS Sleep Disturbance Scale – 6A is assessed at baseline and at in-person visits through week 24. Outcome (e) Sleep Duration Question is assessed at baseline and week 24 only. Outcome (f) Daily NRS is collected daily for the week prior to each study visit and these daily NRS values will be modeled in the analysis. The analysis plan for outcomes (a), (b), and (d), and (f) will be similar to the analysis for aim 2 except that the model will adjust for possible carryover effects in placebo-treated periods that are preceded periods with the active drug treatment. To incorporate the modeling of carryover effects, we will use a modification of model (1):

$$y_{i(s)jkm} = \beta_0 + \gamma_j + \delta_k + \beta_1 X_{i(s)jk} + \lambda_{drg} Z_{i(s)jk,drg} + \beta'_2 \mathbf{w}_{i(s)} + b_s + b_{i(s)} + \epsilon_{i(s)m}, \quad (2)$$

where  $\lambda_{drg}$  is used to model carryover effects with  $Z_{i(s)jk,drg} = 1$  if the treatment at block  $j$ , period  $k - 1$  is drug for patient  $i(s)$  in site  $s$ ; all other terms in the model are defined as in (1). Hypothesis 4 for these measures correspond to  $H_0 : \beta_1 = 0$  versus  $H_a : \beta_1 \neq 0$  from model (2).

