**Aim 5:** The hypotheses under aim 5 are for staircase-evoked pain assessment, serum and synovial fluid levels of chemokines and cytokines; and synovial monocyte chemoattractant protein-1/CCR-2 receptor binding inhibition in blood and synovial fluid. Hypotheses for Staircase-Evoked Pain Assessment, will be tested with the same approaches as for testing the hypotheses under Aim 3 which can accommodate outcomes on participants measured at more than one occasion. For synovial fluid, which is only collected once, the hypothesis testing will use the same approach as for hypotheses under Aim 4 - we will model the week 6 assessment of measures as functions of treatment in the first period, adjusting for sex, age and K-L Grade. The analysis for serum chemokines/cytokines will be more complicated since these measures are obtained at multiple occasions and we want to assess if their impact on pain differs due to treatment in this multi-crossover study. Analytical methods for this complex type of mediation analysis still need to be developed. We will evaluate the impact of the treatment sequence on the change in the WOMAC-A from baseline to V9, modeling serum and synovial fluid levels of chemokines and cytokines as potential mediators of treatment effect by investigating a generalization of the  $2 \times 2$  crossover mediation modeling approaches introduced by (Josephy *et al.*, 2015) and generalized to this multi-crossover trial design.

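### SAP 9.2 Aim 5 gives the serum chemokines and cytokines a still-undeveloped mediation analysis of WOMAC-A instead of the drug-versus-placebo test of marker levels that Hypothesis 4 calls for

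*SAP*

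**What the plan says.** **The hypothesis.** SAP 4.2 states Hypothesis 4 as a treatment effect on the markers: "Compared to placebo, CNTX-6970 300mg BID will result in greater improvement with respect to (a) Staircase-Evoked Pain Assessment; (b) serum and synovial fluid levels". Part (b) refers to the chemokine and cytokine panel. Part (c) adds MCP-1/CCR-2 binding inhibition in blood and synovial fluid. Protocol C.2 and K.2 say the same.

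**The protocol's method.** Protocol K.2, Aim 5: "Hypothesis 4 will be tested with the same approach as for testing the hypotheses under Aim 3". For repeatedly measured outcomes, the Aim 3 approach is the Aim 2 crossover model with one change: "the model will adjust for possible carryover effects in placebo-treated periods that are preceded periods with the active drug treatment". For outcomes measured only at the start and end (PGIC and sleep duration), Aim 3 refers to the Aim 4 regression.

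**The SAP's general method.** SAP 7 applies the mixed-effects crossover model to outcomes measured in several periods. It tests the treatment coefficient by likelihood ratio under both the primary and the secondary objectives.

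**The SAP's specific method.** SAP 9.2, Aim 5, splits the outcomes:
- Staircase pain: "Hypotheses for Staircase-Evoked Pain Assessment, will be tested with the same approaches as for testing the hypotheses under Aim 3".
- Synovial fluid: "For synovial fluid, which is only collected once, the hypothesis testing will use the same approach as for hypotheses under Aim 4".
- Serum chemokines and cytokines: "We will evaluate the impact of the treatment sequence on the change in the WOMAC-A from baseline to V9", with the markers as potential mediators. On the method it says: "Analytical methods for this complex type of mediation analysis still need to be developed".
- Binding inhibition in blood: listed among the Aim 5 hypotheses, with no method assigned afterwards.

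**Sampling.** Protocol F.2.2 draws the serum panel and the blood binding assay at Baseline and Weeks 6, 12, 18 and 24, so each treatment period ends with a value.

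**The concern.** A test of Hypothesis 4 needs the marker as the outcome and drug versus placebo as the comparison. The analysis that 9.2 describes for serum has pain as the outcome, sequence as the exposure and the marker as an intermediate. It asks whether the marker carries part of an effect on pain, not whether the drug moves the marker.

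The reason given for the change does not support it. The same paragraph says that the Aim 3 approach can handle outcomes measured more than once, then treats repeated measurement as what makes the serum analysis harder. A suitable test of the serum levels was therefore already in the plan.

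At stake is which serum result counts as the Hypothesis 4 result: beta1 for each marker (K.2 and SAP 7) or a mediation estimate for WOMAC-A (9.2). If this is left open until the data are unblinded, the choice between two different questions can be made with the results in view. The markers are secondary outcomes that bear on the drug's mechanism, so the answer should be fixed in advance.

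**Working it through.** **1. Passages side by side.** No stated figure is in dispute; the point rests on the text.

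| Hypothesis 4 outcome | Sampling | Protocol K.2 | SAP 7 default | SAP 9.2 Aim 5 |
|---|---|---|---|---|
| Staircase pain | repeated | Aim 3, crossover | crossover | Aim 3 approach: agrees |
| Synovial fluid measures | Week 6 only | Aim 3, which includes the Aim 4 regression | crossover not applicable | Aim 4 approach: no conflict |
| Serum chemokines/cytokines | Baseline, Weeks 6, 12, 18, 24 | Aim 3, crossover | crossover | mediation analysis of WOMAC-A: conflicts |
| Binding inhibition in blood | Baseline, Weeks 6, 12, 18, 24 | Aim 3, crossover | crossover | silent: default applies |

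**2. Text that might fill the gap.** After model (2), SAP 9.2 writes "Hypothesis 4 for these measures correspond to" beta1 = 0. That sentence is in the Aim 3 paragraph and refers to the Aim 3 outcomes, which belong to Hypothesis 2. It is a numbering slip, not the missing serum test. The SAP 7 fallback is triggered by insufficient data, not by an undeveloped method.

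**3. Scope.** Appendix II lists 28 + 27 = 55 analytes. With binding inhibition in blood, 56 outcomes have no drug-versus-placebo test named in 9.2.

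**4. Data available.** Up to 55 × 4 = 220 on-treatment values per marker. Take the SAP's assumed 15% early termination per period. If a subject who stops gives no sample in that period, the total is 46.75 + 39.74 + 33.78 + 28.71 = about 149. If every such subject gives the early-termination sample, it is 55 + 46.75 + 39.74 + 33.78 = about 175. So 149 is a lower bound.

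**5. Cost of the carryover term.** Sequences DPPD and PDDP (SAP 5.3), equal split, n = 55, one value per period, within-subject variance 1, additive block and period effects. The carryover indicator is (0,1,0,0) for DPPD and (0,0,0,1) for PDDP. After removing subject, block and period, the sums per subject are:
- treatment: 1
- carryover: 0.5
- cross-product: −0.5

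Squared correlation = 0.25 / (1 × 0.5) = 0.5, so the variance factor is 1 / (1 − 0.5) = 2.

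- Model (1): Var(beta1) = 1/55 = 0.0182
- Model (2): Var(beta1) = 2/55 = 0.0364

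Detectable difference at 80% power, two-sided 5%, is (1.960 + 0.842) × SE: 0.38 within-subject SD for model (1) and 0.53 for model (2).

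With 15% loss per period (the 149-value case) and a between/within variance ratio (B/W) of 1 to 7, generalised least squares gives Var(beta1) of 0.0277–0.0283 and 0.0534–0.0560. The ratio is 1.92–1.98, and the detectable differences are 0.47 and 0.65–0.66 within-subject SD. If a serial correlation of 0.3 between periods is assumed, the ratio is 2.32 on full data and 2.24–2.30 with dropout.

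**6. Cost in multiplicity.** 56 × 0.05 = 2.8 expected false positives if every null is true.

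**The case against.** **The mediation analysis may be an addition.** SAP 7 is not withdrawn, and 9.2 gives its motive as whether the markers' effect on pain differs by treatment, which is a further question. A mediation analysis also usually contains a treatment-to-marker step. This is a fair reading of intent. But 9.2 assigns explicit tests to staircase pain and synovial fluid and none to serum levels, and it neither writes a treatment-to-marker step nor names one as the test. Saying that the mediation analysis is additional would settle the matter.

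**Sequence is a treatment contrast at V9.** SAP 9.2 notes that the last-period treatment equals the first-period treatment, so sequence does separate drug from placebo at Week 24. That stands, but the outcome is still WOMAC-A and not the marker.

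**Stronger readings a reader might infer.** One is that binding inhibition in blood has no analysis at all. The documents do not support this: 9.2 is silent, and the SAP 7 crossover default applies unopposed. Another is that K.2 requires the crossover model for every part of Hypothesis 4, so that the synovial method is a departure. It is not, because the Aim 3 approach itself includes the Aim 4 regression and synovial fluid is sampled only once.

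**Stakes are modest.** SAP 4.4.3 also treats these markers as potential exploratory biomarkers, and SAP 7 puts estimation ahead of testing. That limits the consequence but does not remove the mismatch.

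**Conclusion.** The point holds for serum chemokines and cytokines. SAP 9.2 as written does not test Hypothesis 4 for the 55 analytes, contrary to Protocol K.2 and the SAP's own section 7. For binding inhibition in blood the defect is an omission that the default covers. Synovial fluid and staircase pain are in order, and the primary endpoint is untouched.

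The size is a matter of scope; no bias or loss of power is claimed. The textual conflict depends on no numerical assumption. The precision figures are illustrative: they assume one value per period, equal allocation and the stated correlation structure, and no document gives a between/within variance ratio for these markers (the values 2, 5 and 7 come from the WOMAC-A sample-size section). For binding inhibition they say little in any case, because the Phase 1 Day 1 means in Protocol A.2.2 were 90.6% on 300 mg BID and 8.9% on placebo.

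The change should be made before database lock.

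**What to change.** In SAP 9.2, Aim 5, state the following:
1. Hypothesis 4 for the serum chemokines and cytokines, and for MCP-1/CCR-2 binding inhibition in blood, is tested by H0: beta1 = 0 in the crossover mixed model on the Week 6, 12, 18 and 24 values. Use the carryover-adjusted model (2), in line with the Aim 3 approach in K.2, with model (1) as a sensitivity analysis.
2. The mediation analysis of WOMAC-A is additional and exploratory.

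In the Aim 3 text, change the hypothesis number attached to model (2) from 4 to 2.

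Optional, and not required by K.2: the baseline marker value as a covariate, and a log transformation fixed in advance.

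**Cost.** One SAP paragraph and one label; no new samples. There are two downsides to state openly. Model (2) roughly doubles the variance of beta1 relative to model (1), although the SAP expects carryover to be gone after four weeks and these samples fall at the end of six-week periods; this is why model (1) belongs alongside it. And 56 unadjusted tests carry about 2.8 expected false positives under the global null, so report estimates with 95% confidence intervals and give individual p-values little weight.
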